1187 shared with the coordinating center, the Jaeb Center for Health Research in Tampa, FL.
1188 De-identified participant information may also be provided to research sites involved in the
1189 study. De-identified participant information may also be provided to Tandem for system
1190 evaluation purposes.

1191 Chapter 8: Statistical Consideration

1192 The approach to sample size and statistical analyses are summarized below. A detailed statistical
1193 analysis plan will be written and finalized prior to the first tabulation of data (i.e., for DSMB
1194 review).

1195 8.1 Objectives

1196 There are three objectives for this study:

- 1197 • Objective 1: Among individuals who used CLC in the Main RCT, to compare continued
1198 use of CLC (t:slim X2 with Control-IQ Technology) for 3 months versus switching to a
1199 Predictive Low-Glucose Suspend (PLGS) system (t:slim X2 with Basal-IQ Technology)
1200 for 3 months.
 - 1201 ○ RCT with 1:1 randomization to intervention with CLC vs. PLGS for 3 months.
1202 All analyses (treatment group comparisons) will be considered
1203 exploratory/hypothesis-generating. Consequently, there will not be an attempt to
1204 adjust for multiplicity. Time-in-range 70-180 mg/dL will be considered the
1205 primary exploratory outcome.
 - 1206 • Objective 2: Among individuals who used SAP in the Main RCT, to obtain additional
1207 safety data by initiating use of the Control-IQ system for 3 months.
 - 1208 ○ Observational study of initiation and use of CLC for 3 months. Safety outcomes
1209 will be tabulated and certain exploratory analyses will be conducted, analyzing
1210 metrics as change from baseline (using SAP) to study period (using CLC).
 - 1211 • Objective 3: To obtain additional safety data by continuing use of the Control-IQ system
1212 until it becomes commercially available
 - 1213 ○ Observational study of initiation and use of CLC for 3 months following use of
1214 PLGS for 3 months. Safety outcomes will be tabulated and certain exploratory
1215 analyses will be conducted, analyzing metrics as change from baseline (using
1216 PLGS) to study period (using CLC).

1217 8.2 Sample Size

1218 The sample size for Objectives 1 and 2 will depend on how many subjects will complete the
1219 prior 6-month Original RCT and consent to participate in the extension. However, it is expected
1220 that about 100 subjects will be enrolled and randomized for Objective 1 and 50 subjects enrolled
1221 for Objective 2.

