1397 assess visit, and phone completion, and study completion rates

- 1398 • Number of and reasons for unscheduled visits and phone calls
1399 • Number of participants who stopped treatment (CLC or PLGS) and reasons
1400

1401 **8.8 Other Tabulations**

1402 Baseline demographic and clinical characteristics will be tabulated by treatment group.

1403 Individual listings of key data for each participant will be created.

1404 The following tabulations and analyses will be performed by treatment group:

- 1405 • Sensor performance metrics (difference, absolute relative difference, and
1406 International Organization for Standardization criteria)
1407 • Sensor use –percent time of use overall and by month
1408 • The daily frequency of downloaded BGM use - overall and by month
1409 • % time CGM data were available to the system – overall and by month
1410 • % time in different operational modes - overall and by month
1411 • Rate of different failure events and alarms per 24 recorded by the system – overall
1412 and by month Among women who consent to collection of the menstrual information,
1413 an analysis that compares outcomes at different times during the menstrual cycle will
1414 be performed overall and by contraception type for selected CGM and insulin
1415 metrics.

1416

1417 **8.9 Planned Interim Analyses**

1418 No interim efficacy analysis is planned.

1419 The DSMB will review safety data at intervals, with no formal stopping rules other than the
1420 guidelines provided in the participant-level and study-level stopping criteria (as defined in
1421 section 6.5 of the protocol).

1422

1423 **8.10 Objective 2 Analyses**

1424 All enrolled subjects will be included in the analyses. Although the primary objective is the
1425 collection of safety data, analyses will be conducted for the outcomes listed above for Objective
1426 1 comparing baseline to follow up using paired t-tests unless the data are highly skewed in which
1427 case a transformation or a robust statistical method will be used instead.

1428 Safety outcomes will be tabulated. Device issues, protocol adherence, and the other variables
1429 listed above for tabulation will be described or summarized as indicated.

1430

1431 **8.11 Objective 3 Analyses**

1432 All enrolled subjects will be included in the analyses. Although the primary objective is the
1433 collection of safety data, analyses will be conducted for the outcomes listed above for Objective

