2.1.1 Endpoints

42

CGM Metrics

43

- 44 Overall Control and Hyperglycemia
 - 45 CGM-measured % in range 70-180 mg/dL.
 - 46 CGM-measured % above 180 mg/dL
 - 47 CGM-measured mean glucose
 - 48 % >250 mg/dL
 - 49 % >300 mg/dL
 - 50 high blood glucose index
 - 51 % in range 70-140 mg/dL
- 52 Hypoglycemia
 - 53 % below 70 mg/dL
 - 54 % below 54 mg/dL
 - 55 % below 60 mg/dL
 - 56 low blood glucose index
 - 57 hypoglycemia events (defined as at least 15 consecutive minutes <70 mg/dL)
- 58 Glucose variability
 - 59 Coefficient of variation (CV)
 - 59 Standard deviation (SD)

60 • CGM metrics by time of day. Calculate all CGM metrics listed above (including the primary
61 outcome) for:
62 ○ All 24 hours of the day
63 ○ Daytime only (06:00AM to 11:59AM)
64 ○ Nighttime only (00:00AM to 05:59AM)

65
66 *HbA1c*

67 • HbA1c at 13 weeks
68 • HbA1c <7.0% at 13 weeks
69 • HbA1c <7.5% at 13 weeks
70 • HbA1c improvement from baseline to 13 weeks >0.5%
71 • HbA1c improvement from baseline to 13 weeks >1.0%
72 • HbA1c relative improvement from baseline to 13 weeks >10%
73 • HbA1c improvement from baseline to 13 weeks >1.0% or HbA1c <7.0% at 13 weeks

74
75 *Questionnaires:*

76 • Fear of Hypoglycemia Survey (HFS-II) at 13 weeks – total score and 3 subscales:
77 ○ Behavior (avoid)
78 ○ Behavior (maintain high BG)
79 ○ Worry
80 • Hyperglycemia Avoidance Scale at 13 weeks – total score and 4 subscales:
81 ○ Immediate action
82 ○ Worry
83 ○ Low BG preference
84 ○ Avoid extremes
85 • Diabetes Distress Scale at 13 weeks – total score and 4 subscales:
86 ○ Emotional burden
87 ○ Physician-related distress
88 ○ Regimen-related distress
89 ○ Interpersonal distress
90 • Hypoglycemia Confidence Scale at 13 weeks – total score
91 • Clarke Hypoglycemia Awareness Scores at 13 weeks

92 • INSPIRE survey scores at 13 weeks
93 • System Usability Scale (SUS) at 13 weeks and final visit – barriers, benefits, and total score
94 • Technology Expectations Survey at baseline (only for participants who had been assigned to SAP
95 during the preceding 6-month RCT) – barriers, benefits, efficacy, and total scores
96 • Technology Acceptance Survey at 13 weeks – barriers, benefits, efficacy, and total scores

97
98
99 *Other*

100 • Insulin at 13 weeks
101 ○ Total daily insulin (units/kg)
102 ○ Basal: bolus insulin ratio
103 • Weight and Body Mass Index (BMI) at 13 weeks

104
105 **2.1.2. Calculation of CGM Metrics:**

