106 • Baseline: CGM data from the last 13 weeks of the preceding 6-month RCT (i.e. 90 days prior to
107 the final visit of the preceding RCT) will be used to calculate baseline metrics. At least 168 hours
108 of CGM data will be required for the calculation. Baseline CGM metrics will be treated as
109 missing for any participants who have fewer than 168 hours of data in the last 13 weeks of the
110 preceding RCT.
111 • Follow-up: CGM metrics will be calculated by pooling all data starting with randomization day
112 in the current study (or enrollment day, for subjects not randomized) and up through previous
113 midnight of the earlier of day 98 from enrollment/randomization or the 13-week visit date, will
114 be included. At least 168 hours of CGM data will be required for the calculation.
115 • All CGM metrics at baseline and during follow-up will be calculated giving equal weight to each
116 sensor reading for each participant.
117 • Daytime and nighttime
118 ○ CGM metrics above will also be calculated for daytime period (06:00AM to 11:59PM)
119 and overnight period (00:00AM to 05:59AM) separately.
120 ○ Minimum 126 hours of CGM data will be required to calculate daytime metrics and
121 minimum 42 hours of CGM data will be required to calculate overnight metrics.
122 ○ If <168 hours of CGM data available for combined day and night, then CGM metrics will
123 not be calculated separately for daytime and overnight periods.

124
125 **2.1.3 HbA1c**

126 • Baseline: Local and lab HbA1c values collected at the 26-week visit in the preceding 6-month
127 RCT will serve as baseline.
128 • Follow-up: Local and lab HbA1c values collected at the 13-week visit will serve as follow-up
129 values.
130 • For continuous outcome models, both local and lab values will be used. For binary outcomes, lab
131 values will be used (if lab value is missing, the local value will be used instead).

133 **2.1.4 Questionnaires**

134 The questionnaires administered at the 26-week visit in the preceding 6-month RCT will serve as
135 baseline, in addition to the Technology Expectations Survey at baseline of the current study for
136 participants who had been assigned to SAP during the preceding 6-month RCT.

137 All questionnaires will be administered online and participants/parents can skip specific questionnaires
138 or items within a questionnaire. All questionnaires will be scored according to the instructions given in

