- 370 • Baseline CGM time 70-180 mg/dL
- 371 • Age at randomization
- 372 • Sex
- 373 • Race
- 374 • Clinical site
- 375 • Body mass index at randomization
- 376 • Income, education, and/or insurance status
- 377 • Baseline scores for quality of life, hypoglycemia awareness and fear questionnaires

378
379
380
381
382 **2.14. Multiple Comparison/Multiplicity**

383 All treatment group comparisons analyses will be considered exploratory/hypothesis-generating.
384 Consequently, there will not be a formal adjustment for multiplicity.

385
386
387 **2.15. Additional Tabulations and Analyses**

388 Twenty-four hours profiles with medians and quartiles lines and 4-week interval boxplots and
389 tabulations by treatment arms for:

- 391 • % below 70 mg/dL
- 392 • % above 180 mg/dL

393 • % time in range 70-180 mg/dL

394 • mean glucose

395

396 Among women who consent to collection of the menstrual information, an analysis that compares
397 outcomes at different times during the menstrual cycle will be performed overall and by contraception
398 type for selected CGM and insulin metrics.

399

400
401

3. Objective 2

402 Among individuals who used SAP in the original RCT, to asses efficacy and to obtain additional safety
403 data by initiating use of the Control-IQ system for 3 months.
404

405 **3.1 Outcome Measures**

406 The outcome measures for this objective will be the same as those listed above in Section 2.1.
407

408 **3.2 General Approach**

409

- 410 • All p-values will be two-sided.
- 411 • Standard residual diagnostics will be performed for all analyses. If values are highly skewed,
412 then an alternate transformation, nonparametric, or M estimation methods will be used instead
413 for the primary and secondary outcomes. Previous experience suggests that no transformation,
414 nonparametric, or M estimation analyses will be necessary for % time in range 70-180 mg/dL, %
415 above 180 mg/dL, mean glucose, or HbA1c. Other outcomes like % below 70 mg/dL over 13
416 weeks are skewed; however the differences from baseline are expected to follow a normal
417 distribution and there may be no need for transformation, nonparametric, or M estimation.
- 418 • All enrolled participants with non-missing baseline and post-enrollment data will be included in
419 the primary and secondary analyses.
- 420 • All before/after comparisons analyses will be considered exploratory/hypothesis-generating.

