421 Consequently, there will not be an attempt to adjust for multiplicity.

422

423 **3.3. Analysis Cohorts**

424 **3.3.1 Per-Protocol Analyses**

425

- 426 • Safety outcomes will be reported for all enrolled participants.
- 427 • If more than 5% of participants have fewer than 50% data (or <1,092hr) of post-enrollment CGM
428 data, then selected CGM analyses will be replicated excluding such participants.
- 429 • Selected CGM and HbA1c analyses will be replicated including only those participants who used
the CLC system for >80% overall.

430
431
432
433

434 **3.4. Primary and other CGM Metrics Analyses**

435

436 This study primary outcome is CGM measured % time in range 70-180 mg/dL over 13 weeks.
437

438 Summary statistics (mean \pm SD or median (quartiles)) will be reported for the CGM metrics and for
439 differences from pre-enrollment.

440 The before/after values will be compared using paired t-tests. Paired differences will be examined for an
441 approximate normal distribution. If the differences are highly skewed, then a Wilcoxon signed-rank test
442 will be used instead.

443

444

445 **3.5. HbA1c Analyses**

446 Summary statistics (mean \pm SD or n(%)) will be reported for the central lab HbA1c (continuous
447 variable) at randomization and 13-weeks. If the central lab values are missing, then the local values will
448 be used instead. The before/after values will be compared using paired t-tests. Paired differences will be
449 examined for an approximate normal distribution. If the differences are highly skewed, then a Wilcoxon
450 signed-rank test will be used instead.

451 For the binary HbA1c outcomes listed above, a McNemar test will be used.

452

453

454 **3.6. Questionnaires, Insulin, Weight, and BMI Analyses**

455 For questionnaires, insulin, weight, and BMI metrics comparisons between before/after will be made
456 using similar methods as described above in Section 3.4 for the primary analysis.

457

458

459 **3.7. Safety Analyses**

460 The safety metrics will be the same as those listed above in Section 2.7 and will be analyzed in a similar
461 manner except that there are no treatment groups for this objective and no formal statistical
462 comparisons.

463

464

465 **3.8. Device Issues**

466 Same as above in Section 2.8, except no randomization and no treatment groups.

467

468

469 **3.9. Protocol Adherence and Retention**

470 Same as above in Section 2.9, except no treatment groups.

471

472

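### Objective 2 plans a McNemar test for four HbA1c outcomes that cannot be scored the same way before and after

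*SAP*

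**What the plan says.** Section 3.5 of the statistical analysis plan, on Objective 2, says "For the binary HbA1c outcomes listed above, a McNemar test will be used". It makes no exceptions. Section 3 has no HbA1c list of its own; section 3.1 says "The outcome measures for this objective will be the same as those listed above in Section 2.1".

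Section 2.1.1 lists six binary HbA1c outcomes:

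- two thresholds at 13 weeks, below 7.0% and below 7.5%;
- three improvements: two absolute, the first being "HbA1c improvement from baseline to 13 weeks >0.5" percentage points and the second using 1.0 as its cut-off, and one relative, "HbA1c relative improvement from baseline to 13 weeks >10" percent;
- one composite, "HbA1c improvement from baseline to 13 weeks >1.0% or HbA1c <7.0% at 13 weeks".

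Baseline is one visit. Section 2.1.3 begins "Baseline: Local and lab HbA1c values collected at the 26-week visit in the preceding 6-month" and takes those values as the baseline.

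Protocol section 8.10 gives no rule for binary outcomes. It speaks of "comparing baseline to follow up using paired t-tests unless the data are highly skewed in which" case a transformation or robust method replaces the t-test.

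**The concern.** McNemar's test compares one yes/no status, defined identically, at two times in the same people. It uses only those whose status changed: 'no' to 'yes' against 'yes' to 'no'.

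An improvement outcome is already a before-to-after comparison. Each participant has one value of it, so there is no pair. The list works in Objective 1, where section 2.5 compares randomized groups by logistic regression. It fails when carried into a single-group paired test.

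The analyst would have to drop these outcomes or invent a before coding, and neither choice would be on record in the plan. The obvious invented coding gives a p-value that counts improvers and ignores people who worsened by the same amount.

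**Working it through.** The documents give no sample size, power or significance level for these tests, so there is no planned figure to reproduce. The first step is structural and needs no assumed numbers.

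**Step 1. Can each outcome be scored the same way at both visits?**

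| Outcome | Status at baseline | Same definition at both visits? |
|---|---|---|
| <7.0% | from the baseline value | yes |
| <7.5% | from the baseline value | yes |
| improvement >0.5% | none (change is 0 by definition) | no |
| improvement >1.0% | none | no |
| relative improvement >10% | none | no |
| >1.0% improvement or <7.0% | only the <7.0% part | no |

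Two outcomes fit. Three have no before status, and one has before and after definitions that differ.

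**Step 2. Improvement outcomes if everyone is coded 'no' before.** The plan does not state this coding; it is the simplest way to make the test run. The 'yes' to 'no' cell is then zero by construction. With k improvers, the exact two-sided p = 2 × 0.5^k:

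- k = 5: 2 × 0.03125 = 0.0625
- k = 6: 2 × 0.015625 = 0.031
- k = 7: 2 × 0.0078125 = 0.016

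At a 0.05 cut-off (assumed), six improvers are enough, however many people worsen.

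**Step 3. How often would that happen with no mean change?** Inputs: n = 50, from Protocol section 8.2 ("that about 100 subjects will be enrolled and randomized for Objective 1 and 50 subjects enrolled" for Objective 2); change ~ Normal(0, SD). The SD is not in the documents, so a range is shown. P(improve) = 1 − Φ(threshold/SD), and the rejection probability is P(k ≥ 6) for a Binomial(50, P(improve)).

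| SD of change | P(improve >0.5) | Expected improvers | P(k ≥ 6), >0.5% | P(k ≥ 6), >1.0% |
|---|---|---|---|---|
| 0.3 | 0.048 | 2.4 | 0.03 | 0.000 |
| 0.4 | 0.106 | 5.3 | 0.44 | 0.000 |
| 0.5 | 0.159 | 7.9 | 0.83 | 0.001 |

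By symmetry, equal numbers are expected to worsen by >0.5%: at SD 0.5, 7.9 against 7.9. At SD 0.8 the >1.0% outcome would reach 0.436, because 1.0/0.8 = 0.5/0.4.

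For >10% relative improvement I used simulation: 20,000 trials per setting, assumed baseline SD 0.9 and mean 7.0 to 8.4, same distribution at both visits. Rejection was 0.000 at SD 0.3, up to 0.008 at SD 0.4, and 0.016 to 0.161 at SD 0.5.

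**Step 4. Composite with before taken as baseline <7.0%.** In the same simulation at SD 0.3 to 0.5 there is no inflation (rejection at most 0.023). At SD 0.8:

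| Baseline mean | Composite | Plain <7.0% |
|---|---|---|
| 7.0 | 0.033 | 0.026 |
| 7.6 | 0.058 | 0.024 |
| 8.0 | 0.104 | 0.019 |
| 8.4 | 0.194 | 0.006 |

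The cause shows in the expected discordant counts at mean 8.4: 6.3 'yes' only after against 2.0 'yes' only before for the composite, but 2.0 against 2.0 for plain <7.0%.

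**The case against.** The strongest reply is that no one would run these tests. A change outcome supplies no pair, so a sensible analyst would test the two thresholds and tabulate the rest, and none of the probabilities above would arise. The table shells are a separate document that was not available, and they may already settle it. That is plausible, but the sentence in section 3.5 prescribes the test for the whole list and would still need correcting.

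A second reply is that 0.83 is not a false-positive rate. With one cell fixed at zero, the hypothesis tested is that nobody improves by >0.5%, and under the stated assumptions that is false. This is right, and it locates the fault: the rejection is correct but says nothing about net change.

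Third, the composite is the weaker case. It can be computed, and the inflation appears only at the larger assumed SD and grows with baseline mean. That also stands, which is why it is counted separately as asymmetric rather than undefined.

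Finally, little depends on these tests. Objective 2 is primarily about safety, section 3.2 labels all before/after comparisons exploratory, continuous HbA1c has its own paired test, and worsening by >0.5% is tabulated through sections 2.7 and 3.7. This limits the severity but does not repair the text.

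**Conclusion.** The concern holds, as a minor one. Of the six planned McNemar tests, two are sound, three are undefined or uninformative, and one compares two different definitions. This follows from the outcome list and the single baseline visit, and needs no assumption about HbA1c.

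The probabilities are illustrations only. They rest on a before coding that the plan does not state, no mean change, a 0.05 cut-off, and SDs and baseline means that the documents do not give. Over an SD of change of 0.3 to 0.5 they run from 0.03 to 0.83 for the >0.5% outcome and stay at or below 0.001 for >1.0%.

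Objective 1 is untouched, since it compares groups by logistic regression. So is Objective 3, since section 4.1.1 lists only the two thresholds.

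**What to change.** Replace the sentence in section 3.5 with: 'For HbA1c <7.0% and HbA1c <7.5%, a McNemar test will be used. The three improvement outcomes (>0.5%, >1.0%, >10% relative) and the composite will be reported as n (%) with an exact 95% CI and no before/after p-value.'

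Limiting the test is the necessary part. As a reporting choice, show the improvement percentages beside the n (%) worsening by >0.5%, so that both directions are visible. Align the table shells if they carry these p-values.

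The cost is wording and four exploratory p-values. No new data are needed, and the continuous HbA1c analysis and Objectives 1 and 3 do not change.
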